6.8.1.2 Analysis

The analyses described in this section consider the primary endpoint, i.e., PD response. Sensitivity analysis of the other estimands are described in the sensitivity analyses section.

Unless stated otherwise, all analyses will be conducted on the FAS.

The study is designed to demonstrate that at least one dose of ACT-246475 enables a large proportion (a target of 85%) of the randomized subjects to achieve a clinically meaningful level of IPA, defined as a PRU < 100.

Hypotheses and statistical model

The primary goal is to determine that the proportion (p) of subjects receiving a dose of ACT-246475, who achieve the PD response as measured by VerifyNow®, is statistically greater than 70%.

To achieve this objective, the testing strategy considers a sequential approach to demonstrate a statistically significant difference between the control arm (placebo) and at least 1 of the active arms, then to confirm that the observed response rate (P_r) in the same active arm is significantly statistically greater than the predefined response rate.

The comparison of each of the 2 active treatment arms will be conducted vs placebo, with the following hypotheses:

$$H_{p0_{HD}}: p_{placebo} = p_{HD} \quad \text{vs} \quad H_{p1_{HD}}: p_{placebo} \neq p_{HD}$$

$$H_{p0_{LD}}: p_{placebo} = p_{LD} \quad \text{vs} \quad H_{p1_{LD}}: p_{placebo} \neq p_{LD}$$

Where, $p_{placebo}$ is the proportion of responders in placebo arm, p_{HD} is the proportion of responders in the ACT-246475 16 mg arm and p_{LD} is the proportion of responders in the ACT-246475 8 mg arm.

Assuming either $H_{p0_{HD}}$, or $H_{p0_{LD}}$, or both are rejected, then the following hypotheses will be tested for each of the active doses that was statistically significantly different from placebo:

$$H_0: P_{responders} = 0.70 \quad \text{vs} \quad H_1: P_{responders} = 0.85.$$

Main analysis

The first set of null hypotheses ($H_{p0_{HD}}$ and $H_{p0_{LD}}$) will be tested each using a 2-sided z-test at an overall significance level (alpha) of 0.025, corresponding to an overall alpha level of 0.05 adjusted for multiplicity using the Bonferroni method.

Each of the second null hypotheses ($H_{0_{HD}}$ and $H_{0_{LD}}$) will be tested by a 1-sided z-test at an overall significance level (alpha) of 0.05 adjusted for multiplicity using the Bonferroni method, i.e., 0.025 for each comparison.

The estimated proportion of responders and the corresponding 95% CI will be provided overall and by injection site, for each treatment arm.

A logistic regression analysis of the PD response will be performed to test for treatment effect (8 mg, 16 mg, and placebo) using the following covariates: injection site (abdomen, thigh), PRU level at randomization (stratification levels), age (continuous), sex (male, female), and assessment time (minutes) as continuous.

A longitudinal analysis of the treatment effect, from start of treatment up to 8 hours after injection, on platelet reactivity as measured by VerifyNow®, i.e., PRU value, will be performed using a mixed model with PRU as the dependent variable, subject as a random factor, and treatment (8 mg, 16 mg, and placebo), injection site (abdomen, thigh), PRU level at randomization (stratification levels), age (continuous), sex (male, female), and assessment time (minutes) as fixed factors. The model will also include

(treatment \times injection site) as an interaction term to assess consistency of treatment effect across injection sites.

IPA as measured by VerifyNow® will also be summarized at each time point as a continuous parameter.

The evolution of PRU values over time will be described using box-and-whisker plots, visualizing mean, median, interquartile ranges, SD, and outliers.

Assuming a treatment \times injection site interaction, summary and graphical analyses described above will be repeated by site injection sub-group.

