3 OVERALL STUDY DESIGN AND PLAN

3.1 Study design

This is a prospective, multi-national, multi-center, double-blind, randomized, placebo-controlled, parallel-group, Phase 2, exploratory study of a single s.c. administration of ACT-246475, at 2 different dose levels, in subjects with stable CAD receiving conventional background therapy (e.g., acetylsalicylic acid, P2Y₁₂ receptor antagonists, etc.).

Approximately 324 adult subjects with stable CAD will be randomized into 1 of the 8 combinations of the treatment, dose, and injection site using a 2:2:2:2:1:1:1:1 ratio as described in [Figure 1](#).

Figure 1 Randomization scheme

Each subject will receive a single s.c. administration of either 8 mg ACT-246475, 16 mg ACT-246475 or matching placebo, either in the thigh or in the abdomen.

Treatment group allocation will be stratified based on baseline platelet reactivity value (expressed as P2Y₁₂ reaction units [PRU]) measured on Day 1 by the VerifyNow® assay before ACT-246475 injection, considering the 3 following categories: high reactivity (PRU > 250), medium reactivity (150 ≤ PRU ≤ 250), and low reactivity (PRU < 150).

No interim analysis is planned for this study.

The study will be conducted at approximately 20 sites and in 5–10 countries (recruitment will be competitive across sites). The list of sites including the name and title of the investigators who are responsible for conducting the trial, and the address and telephone numbers of the trial sites will be filed in the Trial Master File (TMF).

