3.2 Study design rationale

The study design supports the different study objectives, i.e., assessing PD, PK, tolerability, and safety profiles of ACT-246475. The treatment period is justified by the primary objective, which is to characterize the IPA after a single s.c. injection of ACT-246475, either in the thigh or in the abdomen, at 2 different doses in subjects with stable CAD.

The use of 2 doses (i.e., 8 and 16 mg) will allow assessment of the dose/PK and dose/PD relationship in this patient population, which will enrich the results already obtained in a healthy subject population [see Section 5.1.1 for detailed rationale on dose selection].

The stratification by baseline PRU value is implemented in order to account for different levels of P2Y₁₂ inhibition at baseline. The boundaries have been selected to mimic the expected baseline level of P2Y₁₂ receptor inhibition depending on the type of background antiplatelet therapy [Gurbel 2009]: PRU < 150; 150 ≤ PRU ≤ 250; PRU > 250.

The primary PD analysis will be performed with the VerifyNow® method. Results from the VerifyNow® method are well correlated with those obtained with the LTA method [Varenhorst 2009, Gremmet 2015]. The VerifyNow® method has been preferred as it is more standardized than the LTA method; and therefore, less subject to variability in a multicenter study. In addition, the volume of blood required per sample is higher for LTA (6 mL) than for the VerifyNow® method (3 mL). Using the VerifyNow® method will allow assessment of more time points and, therefore, better characterization of the PD profile while requiring less blood withdrawn from the subjects. As LTA remains a reference method and to allow comparison with other trials, some LTA assessments will be performed at selected time points [Table 3].

The use of a double-blind placebo-controlled design is proposed to assess the safety of ACT-246475 compared with placebo and will support additional exploratory analyses. The double-blind design applies to the treatment allocation (i.e., ACT-246475 vs placebo). The knowledge of the dose (8 or 16 mg) and injection site is not expected to affect the primary objective (which is based on objective PD assessment) or the safety evaluation as the study is placebo-controlled. However, to reduce the risks of bias in safety reporting, the dose will be blinded to the subjects (single blind). The injection site will not be blinded in this study.

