4.2 Rationale for the selection of the study population

The population enrolled is expected to reflect the general population of patients with CAD.

Among these patients, those with prior MI are at higher risk of recurrent ischemic events [Fox 2008]. Such patients are treated with acetylsalicylic acid as life-long background therapy. In addition, the American College of Cardiology/American Heart Association and ESC guidelines for the management of patients with STEMI and non-STEMI recommend DAPT for the secondary prevention of recurrent ischemic events for up to 1 year after the acute coronary syndrome (ACS) event, a duration that may be shortened or extended in selected patients if required [Steg 2012; O’Gara 2013; Amsterdam 2014; Roffi 2016; Levine 2016]. The target population for this study will include patients with coronary artery stenosis and patients who have experienced an AMI more than 3 months

prior to randomization. Those patients being candidates for single or DAPT according to guidelines, it is therefore expected to collect sufficient PD and safety data of ACT-246475 on top of antiplatelet therapy including a P2Y₁₂ receptor antagonist.

Ticagrelor and prasugrel are both expected to already provide more than 80% of IPA in patients who are compliant with their treatment [Prasugrel® SmPC, Ticagrelor® SmPC]. It cannot be excluded that, despite treatment with a potent oral P2Y₁₂ receptor antagonist, some patients experiencing an MI still have high on-treatment platelet reactivity and may therefore benefit from ACT-246475.

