6.2 Pharmacokinetic and pharmacodynamic endpoints

6.2.1 Pharmacodynamic endpoints

The primary PD endpoint is the PD response that is defined for each subject as a PRU < 100 starting 30 min after injection and lasting for at least 3 h, as measured via the VerifyNow® assay. This corresponds to inhibition of ADP-induced platelet aggregation (IPA) > 80% [Gaglia 2011, Gremmel 2009, Varenhorst 2009].

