10.3.1 Overall testing strategy

The study is intended to assess the effect of ACT-246475 on platelet aggregation.

The primary null hypotheses will be tested at a 0.025 alpha level for each comparison to placebo, and then, if the null hypothesis is rejected for at least 1 of the 2 active arms, it will be completed by testing in each active arm that the proportion of patients achieving a response is statistically greater than 70%.

The study will be declared to be positive with regard to the primary objective if, for at least 1 of the 2 active arms, the 2 null hypotheses are sequentially rejected at an adjusted alpha level of 0.025.

No imputation will be considered for handling missing values in the main analysis of PD. Imputations may be performed in sensitivity/exploratory analyses, if deemed necessary, e.g., if more than 10% missing values at a given time point.

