6.8.1.4 Subgroup analyses

The consistency of treatment effect across the following subgroups, as defined in protocol section 10.3.2.4, will be assessed by repeating the main analysis on primary PD endpoint, assuming there are enough subjects, i.e., ≥ 20 subjects by subgroup.

- Age: < 55 vs ≥ 55 years
- BMI: < 25.0 vs (≥ 25.0 and < 30.0) vs ≥ 30.0 kg/m^2
- Sex: male vs female
- Diabetes mellitus at baseline: yes vs no
- Chronic kidney disease: yes vs no

PTs to consider for identification of subjects with/without diabetes mellitus, or chronic kidney disease, are described in Section [5.4.4](#).

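### The deciding test against placebo ignores the PRU strata used for randomisation, and no planned analysis separates subjects already below PRU 100 when the response rate is tested against 70%.

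*SAP*

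**What the plan says.** Protocol 3.1: "Treatment group allocation will be stratified based on baseline platelet reactivity value", in three levels (below 150, 150–250, above 250). Protocol 3.2 gives the reason: "The stratification by baseline PRU value is implemented in order to account for different levels of" baseline P2Y12 inhibition.

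Success rests on two tests per dose. The dose-versus-placebo hypotheses "will be tested each using a 2-sided z-test at an overall significance level (alpha) of 0.025" (SAP 6.8.1.2). A dose that passes is then tested one-sided at 0.025 against a 70% response rate. Under Protocol 10.3.1 the study is positive if, for at least one dose, "the 2 null hypotheses are sequentially rejected at an adjusted alpha level of 0.025".

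The strata appear only outside that rule. SAP 6.8.1.2 adds: "A logistic regression analysis of the PD response will be performed to test for treatment effect", with PRU level as a covariate, and a mixed model of PRU values. For PD response itself it plans a proportion with 95% CI per arm, overall and by injection site.

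The responder rule (SAP 6.8.1.1) requires PRU below 100 at 30 min, 1, 2 and 4 h and does not use the pre-dose value. Protocol 4.2 states: "Ticagrelor and prasugrel are both expected to already provide more than 80% of IPA in patients who are compliant with their treatment". Protocol 6.2.1 equates PRU below 100 with IPA above 80%. Consistency across subgroups "will be assessed by repeating the main analysis on primary PD endpoint, assuming there are enough subjects" (SAP 6.8.1.4). The subgroups are age, BMI, sex, diabetes and chronic kidney disease.

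**The concern.** There are two separate points.

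**Test against placebo.** Stratified randomisation balances a factor expected to predict response. An unstratified test then uses a variance that still contains the between-stratum spread, so the standard error is too large and the test falls below its nominal size. The logistic model does not fill the gap. It has no role in the decision, yields an odds ratio rather than a risk difference, and lists assessment time as a covariate although PD response has one value per subject. No risk difference against placebo with a CI is planned.

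**Test against 70%.** SAP 6.8.1.2 makes exceeding 70% the primary goal. This test has no comparator and counts subjects who arrive below PRU 100. The same response rate therefore implies a different drug effect depending on how many such subjects are enrolled. No planned table of PD response shows this: neither pre-dose PRU nor P2Y12 antagonist use is a subgroup, and the lowest stratum mixes subjects below 100 with those at 100–149. SAP 11.1.1 recognises that some subjects start below 100 and redefines the 8 h variable for them, but nothing similar is done for PD response. Protocol 2.2 also lists the impact of concomitant drug use on PD as an objective.

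**Working it through.** **Inputs from Protocol 10.5.** 50% placebo vs 75% active; 70% vs 85% for the second test; 0.025 per dose; 90% power; 98 evaluable and 108 enrolled per arm. The documents give no response rates or sizes by stratum, so all of those below are assumptions.

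**The plan's own sample sizes reproduce.**
- Placebo comparison, log-odds-ratio formula: (2.241 + 1.282)² × [1/(0.5×0.5) + 1/(0.75×0.25)] / (ln 3)² = 95.98, so 96.
- 70% test: [(2.241×√0.21 + 1.282×√0.1275)/0.15]² = 97.98, so 98.
- 98 × 1.10 = 107.8, so 108.

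**Size of the unstratified z-test** (108 per arm, 36 per stratum, placebo 50% overall). The test uses SE = √(2×0.25/108) = 0.0680. With balanced strata the true SE is √(2v/108), where v is the mean of p(1−p) over strata. True size ≈ 2[1 − Φ(2.241 × 0.0680/true SE)].

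| Stratum rates (low/medium/high PRU) | v | True SE | SE too large by | True size |
|---|---|---|---|---|
| 85/45/20% | 0.1783 | 0.0575 | 18% | 0.008 |
| 70/50/30% | 0.2233 | 0.0643 | 6% | 0.018 |
| 60/50/40% | 0.2433 | 0.0671 | 1% | 0.023 |

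Simulation (200,000 trials per scenario) gives 0.008, 0.017 and 0.023. The Cochran-Mantel-Haenszel (CMH) test stays at 0.024–0.025.

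**Power against placebo, 75% vs 50%.** With 85/45/20%: 0.96 (z-test) and 0.98 (CMH). With no stratum effect: 0.948 and 0.947.

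**Which test binds.** The 70% test passes above 0.70 + 1.96×√(0.21/108) = 0.786, so 85 of 108 responders (78.7%) are needed. Against 54 of 108 on placebo, 85 responders give z = 0.287/0.0652 = 4.4, far beyond 2.241. At a 50% placebo rate the 70% test therefore decides. At 65% placebo, 85 responders give z = 0.137/0.0612 = 2.239, just short, so 86 are needed and the placebo test begins to bind.

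**Probability of passing both tests, per dose** (simulated; active rate in each stratum = placebo rate + f × (1 − placebo rate)):

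| Placebo, by stratum | True active | z-test | CMH |
|---|---|---|---|
| 50% (85/45/20%) | 80% | 0.69 | 0.69 |
| 50% (85/45/20%) | 85% | 0.97 | 0.97 |
| 60% (97/60/23%) | 80% | 0.68 | 0.69 |
| 60% (97/60/23%) | 85% | 0.972 | 0.976 |
| 65% (95/65/35%) | 80% | 0.54 | 0.59 |
| 65% (95/65/35%) | 85% | 0.90 | 0.93 |
| 65% (95/35/15%, strata of 60/30/18) | 80% | 0.56 | 0.66 |
| 65% (95/35/15%, strata of 60/30/18) | 85% | 0.93 | 0.97 |

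**Meaning of the 70% result.** Let b be the share responding on background alone, and assume these subjects respond on active too. An overall rate r then means the drug converts (r − b)/(1 − b) of the rest.

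| b (also the placebo rate) | True rate 70% | Smallest result passing both tests |
|---|---|---|
| 0% | 70% | 79% (85/108) |
| 30% | 57% | 70% (85/108) |
| 50% | 40% | 57% (85/108) |
| 65% | 14% | 42% (86/108) |

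**The case against.** An unstratified test after stratified randomisation is valid. Type I error is controlled, power at the planned effect is 0.96 against a target of 0.90, and with weak strata the difference vanishes. The visible loss needs a placebo rate 15 points above plan and an active rate of 80%, which is not a planning value; at the 85% target the loss is 3 to 4 points. All of this stands, and it limits the first point to efficiency and correct size.

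On the 70% test, the plan deliberately enrols subjects on P2Y12 antagonists and asks what share of them reach PRU below 100, so counting background responders is part of the target. The placebo arm shows the background rate alongside. The 14% figure describes a true rate at the null: with 65% placebo and 70% active, both tests pass in only about 0.4–1.0% of trials. This also stands, and the right-hand column of the last table is the fairer guide to a positive result. Even there, conversion ranges from 79% down to 42%.

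Baseline reactivity is partly handled elsewhere. The logistic and mixed models include the strata, the 8 h status splits at a baseline PRU of 100, and LTA-PD response is relative to baseline. None of these tabulates the VerifyNow PD response by pre-dose PRU or by P2Y12 antagonist use, so that gap remains. The three-level CMH test does not close it either, which is why the fix has two parts.

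**Conclusion.** The concern holds on both points, as a recommended improvement rather than a flaw in validity.

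The deciding placebo test does not use the strata the trial randomises on. Its true size lies between 0.008 and 0.023 under the assumed stratum rates, and its standard error is 1% to 18% too large. The success decision is unchanged at the planned 50% placebo rate. At 65% placebo the chance of success falls by 5 to 10 points if the true active rate is 80%, and by 3 to 4 points if it is 85%. That the strata predict placebo response is plausible from the protocol's own rationale but is not quantified there.

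The second point matters more for interpretation. A result just sufficient to pass could mean the drug converts anywhere from 79% to 42% of subjects not already responding, for background response between 0% and 65%, and the planned PD-response tables would not show which. This rests on treating placebo responders as background responders. The documents do not state the share below PRU 100 at baseline.

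**What to change.** 1. In SAP 6.8.1.2, replace the z-test against placebo by a CMH test stratified by the three randomised PRU levels, at the same two-sided 0.025 per dose. Report the Mantel-Haenszel risk difference with a 97.5% CI. Leave the 70% test as it is. Record the change in SAP section 11.1.
2. In SAP 6.8.1.4, add the PD response rate and the difference from placebo in subjects with pre-dose PRU of 100 or more, by PRU stratum, and by baseline oral P2Y12 antagonist use (already derived in SAP 5.4.5). State that the 70% result will be read alongside these.
3. In the same edit, remove or explain the assessment-time covariate in the logistic model of PD response.

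The cost is SAP wording and a few tables from data already collected, with no change to alpha or sample size. If the strata turn out uninformative, the CMH test loses almost nothing (0.947 vs 0.948). The subset estimates will be less precise than the overall ones and should be presented as descriptive.

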1.4 Purpose and rationale of the study

ACT-246475 is a potent, short-acting, reversible, and selective antagonist of the platelet P2Y₁₂ receptor, which is a validated target for the treatment and prevention of arterial thrombosis. ACT-246475 has shown a favorable PK/PD and safety profile in animal models, confirmed in studies conducted in healthy subjects. This Phase 2 study is conducted in subjects with atherosclerotic disease to generate data which are critical for dose selection in future clinical trials in the target AMI population. The impact of 2 different doses and 2 different sites of injection (abdomen vs thigh) on the PD, PK, safety and tolerability of ACT-246475 will be assessed.

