10.5 Sample size

The sample size is based on the primary PD endpoint, which is the proportion of subjects achieving a predefined PD response as measured by VerifyNow®. The computation of the sample size was performed using the East 6.0 software (version 6.4.0.1, 30 Aug. 2016) from Cytel.

This study includes 3 treatment arms, 2 active arms (ACT-246475 8 mg and 16 mg) and a placebo arm comprising the 2 dose-matching placebo groups.

The primary objective is to assess the effectiveness of ACT-246475 to allow subjects to achieve a predefined PD response, therefore the sample size will be provided in order to reach the necessary power to sequentially demonstrate that at least 1 of the 2 doses has a higher response rate than placebo and that this response rate is statistically significantly greater than the proportion of responders under H_0 .

The sample size required for demonstrating a difference to placebo is based on an overall alpha of 0.05 (2-sided), adjusted for multiplicity using a Bonferroni method to 0.025 for each comparison, and a power of 0.9; the assumptions related to response rate under the null and alternative hypotheses are reported in the table below:

Proportion of responders under H_0 (placebo)	Proportion of responders under H_1 (active)	Number of subjects (total)	Number of subjects (per arm)
50%	75% (odds ratio of 3)	288	96

The sample size required to demonstrate that the achieved response rate is different from 70% is based on a 2-sided type I error (alpha) of 0.025, and a power of 0.9; the assumptions related to response rate under the null and alternative hypotheses, are reported in the table below:

Proportion of responders under H_0	Proportion of responders under H_1	Number of subjects (total for the 2 active arms)	Number of subjects (per arm)
70%	85%	196	98

Therefore the study should include at least 98 subjects evaluable for the primary PD endpoint in each treatment arm. Assuming a rate of drop-out or non-evaluable data of about 10%, each arm will include 108 subjects leading to a total for the study of 324 subjects.

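### The fixed 0.025-per-dose split is valid but leaves alpha unused once one dose has passed both tests; passing it to the other dose would modestly raise per-dose power (optional improvement)

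*SAP*

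**What the plan says.** SAP 6.8.1.2 (Main analysis) sets up two steps for each dose, and in both steps the level is "adjusted for multiplicity using the Bonferroni method".

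- **Step 1, dose against placebo:** a "2-sided z-test at an overall significance level (alpha) of 0.025, corresponding to an overall alpha level of 0.05" before the split between doses.
- **Step 2, response rate above 70%:** run "for each of the active doses that was statistically significantly different from placebo". Each of these hypotheses "will be tested by a 1-sided z-test at an overall significance level (alpha) of 0.05", which the SAP then halves to 0.025 per dose.

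Protocol 10.3.2.1 gives the same levels. Under Protocol 10.3.1 the study is positive if, "for at least 1 of the 2 active arms, the 2 null hypotheses are sequentially rejected at an adjusted alpha level of 0.025". Neither document lets a dose that has completed its sequence pass its alpha to the other dose.

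On purpose, Protocol 1.4 says the study will "generate data which are critical for dose selection in future clinical trials in the target AMI population", and Protocol 5.1.1 says the two doses should allow modelling of the phase 3 dose.

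**The concern.** The two 0.025 shares add up to the 0.05 budget. Once one dose has rejected both its hypotheses, its share has no further use under the plan, while the other dose is still held to 0.025. Under a Holm-type rule the second dose could then be tested at 0.05 without exceeding the budget.

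What is at stake is only the formal conclusion on the second dose. The study-level verdict cannot change, because alpha is passed on only after one dose has already passed. The per-dose conclusion has some value in a study meant to inform dose selection: Protocol 5.1.1 chose the two doses on different criteria (duration of inhibition for the low dose, limited residual effect at 8 h for the high dose), so it is informative whether one or both exceed 70%.

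**Working it through.** **1. Inputs.** Levels and order of testing: SAP 6.8.1.2 and Protocol 10.3.2.1. Planning rates (Protocol 10.5): placebo 50% against active "75% (odds ratio of 3"), and 70% against 85%. Sample size: 98 evaluable and 108 enrolled per arm (Protocol 10.5). Allocation is 1:1:1 once the placebo groups are pooled.

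**2. The plan's own figures reproduce.**

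- Placebo comparison (Wald test on the log odds ratio): n = (z₀.₉₈₇₅ + z₀.₉₀)² × (1/0.25 + 1/0.1875) / (ln 3)² = (2.2414 + 1.2816)² × 9.333 / 1.2069 = 95.98, so 96.
- 70% test: n = [(2.2414 × √0.21 + 1.2816 × √0.1275) / 0.15]² = 97.98, so 98.
- Enrolment: 98 × 1.10 = 107.8, so 108.

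The 98 uses a two-sided 0.025 (0.0125 in the upper tail), whereas the test is to be run one-sided at 0.025.

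**3. Why passing alpha on is valid.** Start with 0.025 on each placebo hypothesis. A rejected placebo hypothesis passes its 0.025 to the 70% hypothesis of the same dose. A rejected 70% hypothesis passes it to the other dose. This is a Bonferroni-Holm graphical procedure, so the nominal family-wise error stays at 0.05. The alpha may move only after **both** hypotheses of a dose are rejected; until then that dose needs it for its own 70% test.

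**4. What changes at the cutoff.** The 70% test rejects when the observed rate exceeds 0.70 + z × √(0.21/n).

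- n = 98: one-sided 0.025 gives 0.7907 × 98 = 77.5, so 78 responders; one-sided 0.05 gives 0.7761 × 98 = 76.1, so 77.
- n = 108: 0.7864 × 108 = 84.9, so 85; 0.7725 × 108 = 83.4, so 84.

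The cutoff moves by one responder in each case.

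**5. Power.** Simulation with 1,000,000 trials per scenario, a shared placebo arm at 50%, a pooled two-sided z-test for step 1 and a one-sided z-test with null variance for step 2. Each cell shows fixed split → alpha passed on.

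| True rates of the doses | Outcome | n = 98 | n = 108 |
|---|---|---|---|
| 85% and 85% (planned) | a given dose passes both tests | 94.5% → 96.7% | 97.1% → 98.3% |
| 85% and 85% | both doses pass | 89% → 94% | 94% → 97% |
| 85% and 85% | at least one dose passes | 99.7%, unchanged | 99.9%, unchanged |
| 90% and 80% (assumed) | the 80% dose passes | 60% → 69% | 68% → 76% |
| 85% and 75% (assumed) | the 75% dose passes | 17.5% → 24% | 22% → 29% |

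**6. Error actually spent.** With both doses at 70% the family-wise error is the same under both rules, because a first false claim occurs at 0.025 either way. The informative cases have one effective dose and one null dose.

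| True rates | n = 98 | n = 108 |
|---|---|---|
| 95% and 70% | 2.2% → 3.8% | 2.8% → 4.5% |
| 95% and 50% (equal to placebo) | 2.7% → 5.4% | 2.4% → 4.8% |

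The 5.4% comes from discreteness of the z-test at a nominal 0.05. The fixed plan shows the same effect: 5.5% at n = 108 with both doses at 70%.

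**7. Agreement with the reported interval.** SAP 6.8.1.2 reports a 95% CI for each arm without naming the method. At 77/98 (78.6%) a one-sided 0.05 test declares the rate above 70%, but the lower 95% limit is 69.5% (Wilson) or 69.1% (exact). The Wald limit is 70.4%.

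**The case against.** The strongest reply is that nothing here is wrong. The fixed split controls the stated error rate and is described consistently in both documents. The aim in SAP 6.8.1.2 is to show that at least one dose works, and that probability is identical under both rules. No section makes dose selection depend on a per-dose significance verdict: Protocol 5.1.1 refers to modelling, response rates with intervals are reported for every arm regardless, and Protocol 3.1 calls the study exploratory. All of this stands, and it is why the point is optional.

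A reader might go further in three ways that the documents do not support.

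- **That the split is an error or leaves the study short of power.** It does not: 96, 98 and 108 reproduce, and at 85% a given dose already passes both tests with 94.5% probability at 98 per arm.
- **That a dose meeting the target is likely to be left without a conclusion.** The target in both documents is 85%, where the gain per dose is about 2 points at 98 per arm. The 9-point gain needs a true rate of about 80%, which neither document states.
- **That the change is free.** It costs nothing in sample size, in power for the first dose or in nominal error control. But the error spent on a null second dose rises towards the 0.05 already budgeted, a claim at the higher level may disagree with the 95% CI, and the protocol also fixes 0.025, so the change is a departure that must be recorded and justified.

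**Conclusion.** The point holds as an efficiency gain, not as the correction of a flaw. Passing on the alpha is never less powerful than the fixed split, and it leaves the sample size and the study-positive rule untouched. At the planned 85% the power for a given dose rises by about 2 points at 98 per arm and about 1 point at 108; the power for both doses rises by about 4 points (89.2% to 93.6%) and about 2 points (94.3% to 96.7%). Larger gains of 8 to 9 points depend on an assumed 80% second dose.

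These figures assume placebo at 50%, the z-tests as the SAP describes them, and a one-sided 70% test. If that test were instead kept two-sided, as it was sized, per-dose power at 85% would rise from 90.9% to 94.1% (n = 98) and from 91.9% to 96.6% (n = 108).

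**What to change.** Before unblinding, add to SAP 6.8.1.2:

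> If both null hypotheses are rejected for one dose at 0.025, the other dose is tested in the same two-step order at 0.05 (2-sided against placebo, then 1-sided against 70%); the study-positive rule is unchanged.

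Two things go with it.

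1. Record and justify the change in SAP 11.1, since Protocol 10.3.1 and 10.3.2.1 fix 0.025 per dose. State there that the 70% test is one-sided, because Protocol 10.5 sized it two-sided.
2. For a claim made at the higher level, report the confidence bound that matches that level (a one-sided 95% lower bound for the 70% test) beside the two-sided 95% CI.

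The cost is a short text change and one extra bound in the outputs. No data, visits or subjects are added. If the sponsor prefers the simpler rule, the plan is sound as it stands.
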